12.0 Study Timelines

12.1 Describe the anticipated duration needed to enroll all study subjects.

Response: 18 months from the start date of funding (October 1st, 2018)

The post-training assessment will be completed by September 28th, 2021.

12.2 Describe the duration of an individual subject's participation in the study. Include length of study visits, and overall study follow-up time.

Response: Once enrolled in the study the participant will be administer baseline assessment protocols that combined will take approximately 2 hours. The individual will then perform 12 sessions (3 per week – Monday, Wednesday, and Friday) of HIIT exercise. The exercise protocol plus body weight and blood pressure measurements will take no more than 20 minutes. A final assessment will also take approximately 2 hours. Participants in the post-HIIT examination will be required to participate for one additional visit.

12.3 Describe the estimated duration for the investigators to complete this study (i.e. all data is collected and all analyses have been completed).

Response: Two years from the enrollment of the last participant. Post-HIIT assessment will require three months to complete.

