1.0 Objectives

1.1 Describe the purpose, specific aims, or objectives of this research.

Response: The purpose of this proposed work is to assess the feasibility of recruiting and administering a short session high intensity interval training regimen to older adults (60-90 years of age), as well as performing routine physical performance and quality of life assessments, and obtain blood samples for analysis of inflammatory biomarkers, testosterone, and serum microRNA.

After 20-months of COVID-19 restrictions, we will contact previously enrolled participants and ask them to return for 1 follow-up visit in order to investigate changes in physical fitness, muscle strength, physical activity, functional capacity, and microRNA profiles among participants who completed our short-session high intensity interval training program, 16-months previously. This will be conducted to explore possible de-training-associated loss of fitness, function, and quality of life among participants who previously completed a 12-week HIIT intervention.

1.2 State the hypotheses to be tested, if applicable.

NOTE: A hypothesis is a specific, testable prediction about what you expect to happen in your study that corresponds with your above listed objectives.

Response: We hypothesize that we will demonstrate adequate recruitment rates and low attrition rates such that we can justify future studies designed to demonstrate the benefits of HIIT in older populations.

We also hypothesize that participants who complete 12-weeks of HIIT and then become sedentary over the following 16-months will demonstrate reduced fitness, function, and quality of life, along with alterations in key underlying biological processes.

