5.0 Study Design

- 5.1 *Describe and explain the study design (e.g. case-control, cross-sectional, ethnographic, experimental, interventional, longitudinal, observational).*

Response: The study is an interventional study that examines physical performance, functional capacity, quality of life, and physiologic parameters before and after a 3-month short session high intensity interval training regimen. The exercise regimen will be tailored to the individual based upon watts generated at VO₂max determined during maximal respiratory analysis. The regimen will be a total of 11.5 minutes that includes: a 30 second warm-up at a watts value that corresponds to 25% of VO₂max, and then 3 minutes continued warm-up at the watts value at 50% VO₂max, then 3 intervals of 1-minute at the watts value at 80% VO₂max then 1-minute active recovery at the watts value at 50% VO₂max, and then ending with 1-minute at the watts value at 80% VO₂max and one final minute at 10 watts for cool down.

Parameters include:

Frailty using the Fried physical frailty scale [1], that includes grip strength, gait speed (15-foot test), body weight change, and survey questions for endurance and activity levels.

Functional capacity using the SPPB that includes a chair rise test, balance and coordination testing, and a gait speed test. We will also conduct surveys to assess activities of daily living (ADLs) and the quality of life, enjoyment, and satisfaction questionnaire – short form (Q-LES-Q-SF) during consultation to assess general well being and perceived quality of life. We will also conduct the physical activity enjoyment scale (PACES) survey [43] to determine the participant's perceived enjoyment of the exercise protocol.

Serum inflammatory profile: While frailty is correlated with high levels of the pro-inflammatory serum markers C reactive protein and interleukin-6, regular exercise can attenuate inflammation [47]. Of particular interest, HIIT reduced pro-inflammatory IL-6 expression in obese subjects. Given the significance of inflammation in both frailty and exercise, we will examine the baseline and endpoint serum inflammatory profiles for changes in C reactive protein, interleukin-6, and the anti-inflammatory interleukin-10 using multiplex ELISA analysis (Millipore).

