Physiologic status: We will assess several indicators of physiologic health including body weight, pulse rate and blood pressure (before and after exercise sessions), quadriceps strength and biceps strength (microFET2 digital handheld dynamometer – device is placed on the lower leg of participant as the individual is asked to lift leg – or the wrist as the individual is asked to lift their forearm), and maximal oxygen uptake (VO2max). The VO2max test is a symptom limited maximal incremental cardiopulmonary exercise test on an electronically braked cycle ergometer. After one minute of unloaded cycling, workload is increased by a fixed amount each minute (ramp protocol) until the subject has to stop due to dyspnea or leg fatigue.

Regional Tissue Oxygen Saturation: fNIRS will be used to measure blood flow to each subject's exercising quadriceps muscle. The fNIRS device will be strapped atop the right quadriceps muscle using a neoprene sleeve prior to the VO2max test and will remain in place through cessation of exercise and recovery. The fNIRS device communicates wirelessly via Bluetooth to a laptop computer for data acquisition. The fNIRS device is both small (~5 cm x ~7 cm x ~2.5 cm) and non-invasive.

Exercise protocol: The high intensity interval training (HIIT) regimen will be a 11.5 minute program featuring a 30-second warm up (at 25% of the watts at VO2max), an additional 3-min warm up (50% VO2max), followed by 3 intervals of 1 min high intensity (80% VO2max), then 1 min recovery (50% VO2max), one additional 1-min interval at high-intensity (80% HRmax), and then a final minute at cool down (10 watts). The programs will be given 3 days a week for 12 weeks total, with intensity increase the greater of 5% or 5 watts for each speed every 2 weeks. The participant may be asked to do an additional 1-2 sessions at the completion of 36 sessions if their last session happens to fall on a Monday or Wednesday. Additionally, a Borg scale (essentially a 1-10 scale) will be used to determine breathlessness, fatigue, and overall difficulty of the HIIT regimen and the intensities will be decreased 5 watts if individuals score an 8 or higher in any of these categories and increased the greater of 5 watts or 5% if individuals score 3 or less in all categories. The HIIT regimen will be performed on a Matrix R3x recumbent exercise bikes.

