22.0 Risks to Subjects

22.1 List the reasonably foreseeable risks, discomforts, hazards, or inconveniences to the subjects related to their participation in the research. Consider physical, psychological, social, legal, and economic risks. Include a description of the probability, magnitude, duration, and reversibility of the risks.

NOTE: Breach of confidentiality is always a risk for identifiable subject data.

Response: The methodology is relatively low risk to participants, with the highest risk methods being blood draw, a maximal respiration test, and 36 exercise sessions (plus 1-2 optional sessions) over a 12 week period. Additionally, participants will be asked to travel to the Buffalo VAMC for assessments and exercise sessions, which thus includes the risk of transit. The overall probability of adverse events is low and in all but the most rare events, harm will be reversible.

22.2 Describe procedures performed to lessen the probability or magnitude of risks, including procedures being performed to monitor subjects for safety.

Response: We will perform safety monitoring of participants as necessary to minimize risk of harm.

22.3 If applicable, indicate which procedures may have risks to the subjects that are currently unforeseeable.

Response: Exercise testing and training carries inherent risks that may vary from participant to participant.

22.4 If applicable, indicate which research procedures may have risks to an embryo or fetus should the subject be or become pregnant.

Response: Not applicable.

22.5 If applicable, describe risks to others who are not subjects.

Response: Not applicable.

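### Do the conflicting session counts (12 versus 36) and the mixed intensity unit for the last interval affect who counts as a completer, or any result?

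*Combined protocol and SAP*

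**What the plan says.** **Number of sessions.** Protocol section 12.2, on how long a subject takes part, states "The individual will then perform 12 sessions (3 per week". Section 11.1, which describes the exercise protocol, states "The programs will be given 3 days a week for 12 weeks total" and, when explaining when extra visits may be added, refers to "additional 1-2 sessions at the completion of 36 sessions". Section 22.1, on risks, gives "36 exercise sessions (plus 1-2 optional sessions) over a 12 week period". Sections 2.1 and 5.1 describe a 3-month intervention, and section 8.6 refers to 3 to 4 months of travel.

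**Last high-intensity minute.** Section 5.1 describes the sequence as "and then ending with 1-minute at the watts value at 80" per cent of VO2max. Section 11.1 has "one additional 1-min interval at high-intensity (80% HRmax" for the same minute, although it sets the three preceding intervals at 80% VO2max.

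**Where completion appears.** Section 1.1 directs the follow-up to changes "among participants who completed our short-session high intensity interval training program, 16-months previously", and the same paragraph gives the intervention's length as 12 weeks. The hypothesis in section 1.2 concerns "participants who complete 12-weeks of HIIT and then become sedentary over the following 16-months". Section 3.0 also uses a 12-week program. Section 6.1 says that 27 subjects will have their final visit and that recruitment is closed.

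**The concern.** Twelve and 36 sessions are very different amounts of training, and the pilot is meant to inform later studies (sections 1.2 and 18.1). If completion were judged by sessions attended, a person who stopped after 12 to 35 sessions would be a completer under section 12.2 but not under section 11.1. The follow-up group could then depend on which section the analyst happened to read. Attrition is part of the primary aim in section 2.1, so it too might seem exposed.

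The interval unit raises a different worry. A percentage of HRmax and a watts value tied to VO2max are different prescriptions, and the template note in section 11.1 asks for enough detail to replicate the study. A reader cannot tell from the two sections which one governed the last minute.

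**Working it through.** **1. The count.** Inputs: 3 sessions per week (sections 11.1 and 12.2), 12 weeks (sections 11.1 and 22.1), 12 sessions (section 12.2).

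- 3 per week × 12 weeks = 36 sessions. This reproduces the figure in sections 11.1 and 22.1.
- 12 sessions ÷ 3 per week = 4 weeks. This does not match the 12-week or 3-month length given in sections 1.1, 1.2, 2.1, 3.0, 5.1, 11.1 and 22.1.

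Section 12.2 therefore stands alone against the document's other figures.

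**2. The exposure implied by each count.** Inputs: the segments in sections 5.1 and 11.1.

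- Session length: 0.5 + 3 + 3 × (1 + 1) + 1 + 1 = 11.5 min, which reproduces the stated 11.5 min.
- High-intensity minutes per session: 3 + 1 = 4.

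| Sessions | Total minutes | High-intensity minutes |
|---|---|---|
| 12 | 12 × 11.5 = 138 | 12 × 4 = 48 |
| 36 | 36 × 11.5 = 414 | 36 × 4 = 144 |

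The ratio is 3. Because the segment times add up correctly, the VO2max/HRmax conflict concerns only the intensity label, and only 1 of the 4 high-intensity minutes.

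**3. What a session-based completion rule would do.** This is hypothetical. The base of 27 comes from section 6.1. The documents give no attendance data, so the number of people affected is an assumption.

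- Attendance counts classified differently: 35 − 12 + 1 = 24.
- Each affected person moves the completed proportion by 1/27 = 3.7 percentage points.
- For 0, 1, 3 or 5 affected: 0, 3.7, 11.1 or 18.5 points.

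**4. Whether the protocol contains such a rule.**

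- Sections 1.1, 1.2 and 3.0 state completion as 12 weeks. Twelve sessions at the stated frequency end at week 4, so stopping there does not meet a 12-week description, whatever number section 12.2 prints.
- Section 12.2 describes time commitment and sets no condition for having finished the sessions.
- The mention of 36 sessions in section 11.1 explains when 1 or 2 visits may be added because of the weekday on which the last one falls. It is a scheduling remark, not an attendance threshold.
- Section 1.1 says previously enrolled participants will be contacted, and section 6.1 names the 27 subjects. Neither filters by sessions attended.

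The figures in step 3 therefore rest on a threshold that the protocol does not contain.

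**5. Whether any analysis uses the count or the unit.**

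- Section 18.1 compares baseline with endpoint by paired t-test for SPPB, ADLs, Q-LES-Q-SF, quadriceps strength, VO2max, inflammatory markers and testosterone. Sessions attended is not a variable, covariate or selection rule.
- Section 20.3 defines safety limits from blood pressure, heart rate and self-reports. None uses the planned number of sessions or the intensity unit.
- Section 2.1 names attrition without tying it to a share of planned sessions.

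**The case for a change.** The strongest case for acting is that a guess does not correct a controlling document. Section 12.2 is a complete sentence in the current text, the planned exposure differs threefold, and the follow-up visit had not yet taken place when this version was written. On the interval, the HRmax label cannot be dismissed as obviously wrong, because section 11.2 lists a maximum heart rate score from the VO2max test among the data collected, so either unit could have been meant. An update of the protocol and consent form is already announced in section 6.1, so correcting the wording would cost almost nothing.

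Much of this stands. The contradictions exist, the documents alone do not settle the interval unit, and the report will need one description of the regimen. What does not stand is the step from inconsistent wording to an inconsistent follow-up group. That step needs a session threshold, and none is stated. Adding one now would impose a session-based definition on an objective written in weeks, after attendance is already known. That would be a new post hoc choice, not a repair. The lack of a detailed definition of completion or attrition is a gap of its own, and correcting the count in section 12.2 would not fill it. Analysts can work from the stated 12-week length and report the sessions attended alongside it. Section 20.5 has safety data collected at every exercise session, so attendance should be recoverable from study records without relying on the protocol's planned number.

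**Conclusion.** The concern is right about the text and wrong about the consequence. The documents contradict themselves on the number of sessions (12 against 36, or 4 weeks against 12) and on the unit for 1 of 4 high-intensity minutes. These passages must be reconciled. Which version applies is for the investigator, and no view is taken here.

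No effect on the follow-up group, on attrition or on any planned comparison is shown. The 3.7 points per participant would arise only under a session-based completion rule that the protocol does not have, and the number of people it would touch is unknown and may be zero.

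This rests on three readings. Training is over, since the follow-up looks back 16 months to its end. Completion means the 12-week length that sections 1.1, 1.2 and 3.0 state. Attrition is not counted against a planned number of sessions, because nothing says it is. On those readings this is a clerical matter for the wording and the report, and correcting it would not alter what the trial does or concludes.

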13.0 Setting

13.1 Describe all facilities/sites where you will be conducting research procedures. Include a description of the security and privacy of the facilities (e.g. locked facility, limited access, privacy barriers). Facility,

department, and type of room are relevant. Do not abbreviate facility names.

NOTE: Examples of acceptable response may be: "A classroom setting in the Department of Psychology equipped with a computer with relevant survey administration software," "The angiogram suite at Buffalo General Medical Center, a fully accredited tertiary care institution within New York State with badge access," or, "Community Center meeting hall."

Response:

- Subject interaction inclusive of obtaining consent, blood draw, functional capacity assessments, surveys, will take place in room 827B in the VA medical center and nearby hallways (for gait speed test)
- Exercise sessions will take place in room 823-B2 in the VA-medical center.
- Isolation of serum miRNA and analysis of serum inflammatory biomarkers will be performed in [name] laboratory in building 20 of the VA.
- Measurements of testosterone will be performed as a service by Quest Diagnostics.
- Sequenced miRNA data will be generated by the NYS Center of Excellence in Bioinformatics and Life Sciences.

13.2 For research conducted outside of UB and its affiliates, describe:

- *Site-specific regulations or customs affecting the research*
- *Local scientific and ethical review structure*

NOTE: This question is referring to UB affiliated research taking place outside UB, i.e. research conducted in the community, school-based research, international research, etc. It is not referring to multi-site research. UB affiliated institutions include Kaleida Health, ECMC, and Roswell Park Cancer Institute.

Response: N/A: This study is not conducted outside of UB or its affiliates.

14.0 Community-Based Participatory Research

14.1 Describe involvement of the community in the design and conduct of the research.

NOTE: Community-Based Participatory Research (CBPR) is a collaborative approach to research that equitably involves all partners in the research process and recognizes the unique strengths that each brings. CBPR begins with a research topic of importance to the community, has the aim of combining knowledge with action and achieving social change to improve health outcomes and eliminate health disparities.

Response: N/A: This study does not utilize CBPR.

14.2 Describe the composition and involvement of a community advisory board.

Response: **N/A:** This study does not have a community advisory board.

15.0 Resources and Qualifications

*15.1 Describe the qualifications (e.g., education, training, experience, expertise, or certifications) of the Principal Investigator **and** staff to perform the research. When applicable describe their knowledge of the local study sites, culture, and society. Provide enough information to convince the IRB that you have qualified staff for the proposed research.*

NOTE: If you specify a person by name, a change to that person will require prior approval by the IRB. If you specify a person by role (e.g., coordinator, research assistant, co-investigator, or pharmacist), a change to that person will not usually require prior approval by the IRB, provided that the person meets the qualifications described to fulfill their roles.

Response: All local research staff has completed CITI training. All research staff has extensive experience conducting clinical trials.

The physicians conducting the research specialize in exercise rehabilitation programs and have conducted similar clinical trials.

Describe other resources available to conduct the research.

15.2 Describe the time and effort that the Principal Investigator and research staff will devote to conducting and completing the research.

NOTE: Examples include the percentage of Full Time Equivalents (FTE), hours per week. The question will elicit whether there are appropriate resources to conduct the research.

Response:

25% of PI effort

10% of each co-investigators' effort

10 hours weekly for each of the research assistants

15.3 Describe the availability of medical or psychological resources that subjects might need as a result of anticipated consequences of the human research, if applicable.

NOTE: One example includes: on-call availability of a counselor or psychologist for a study that screens subjects for depression.

Response: Procedures will be performed at the Buffalo VA medical center (VAMC). Additionally, the laboratory is equipped with oxygen and one automatic electronic defibrillator. During the maximal exercise tests, a physician will be present. In case of an emergency, procedures are in place to expedite medical care. All staff will be CPR and first aid certified.

15.4 Describe your process to ensure that all persons assisting with the research are adequately informed about the protocol, the research procedures, and their duties and functions.

Response: All study staff are trained on the study protocol by first reviewing the protocol itself in detail. The PI conducts a training session to ensure that the research team understands the protocol and each individual's responsibility. A major focus of training will be to ensure that confidentiality measures are in place and will be followed.

16.0 Other Approvals

16.1 Describe any approvals that will be obtained prior to commencing the research (e.g., school, external site, funding agency, laboratory, radiation safety, or biosafety).

Response: IRB approval must be obtained before study initiation, no other approvals are required

17.0 Provisions to Protect the Privacy Interests of Subjects

17.1 Describe how you will protect subjects' privacy interests during the course of this research.

NOTE: Privacy refers to an individual's right to control access to him or herself. Privacy applies to the person. Confidentiality refers to how data collected about individuals for the research will be protected by the researcher from release. Confidentiality applies to the data.

Examples of appropriate responses include: "participant only meets with a study coordinator in a classroom setting where no one can overhear", or "the participant is reminded that they are free to refuse to answer any questions that they do not feel comfortable answering."

Response: Study procedures are performed in private exam areas. Study procedures are performed only by study staff. The participants will be reminded that they are free to refuse to answer any questions that they do not feel comfortable answering

17.2 Indicate how the research team is permitted to access any sources of information about the subjects.

*NOTE: Examples of appropriate responses include: school permission for review of records, consent of the subject, HIPAA waiver. This question **does apply** to records reviews.*

Response: Existing records will be reviewed after obtaining informed consent from the selected participants.

